#### **6.1.4. Prior and Concomitant Medications**

Concomitant medications including rescue medication will be coded using both the GSK Drug and WHO Drug dictionaries. However, the summary will be based on GSK Drug dictionary only. The summary of concomitant medications will be provided by ingredient, i.e. multi-ingredient medications will be summarized for each individual ingredient rather than a combination of ingredients. The summary will be created using ingredient base names, i.e. ingredients with the same base name but different salt will appear under one base name in the summary.

Concomitant medications include any medication that was taken at some point during the on-intervention period as defined Section [6.3.2](#).

Prior medications will be included in listings.

#### **6.1.5. Study Intervention Compliance**

Frequencies and percentages for number of days dosed will be presented.

**6.2. Appendix 2 Electronic Clinical Outcome Assessment  
(eCOA) Compliance**

Not Applicable

### 6.3. Appendix 3 Data Derivations Rule

#### 6.3.1. Criteria for Potential Clinical Importance

Reference ranges for all laboratory parameters collected throughout the study are provided by the laboratory. A laboratory value that is outside the reference range is considered either high abnormal (value above the upper limit of the reference range) or low abnormal (value below the lower limit of the reference range). Note: a high abnormal or low abnormal laboratory value is not necessarily of clinical concern.

In addition, the following criteria will be used to flag potential clinical importance:

##### 6.3.1.1. Laboratory Values

Haematology				
Laboratory Parameter	Units	Category	Potential Clinical Concern Range	
			Low Flag (< x)	High Flag (>x)
Haematocrit	Ratio of 1	Female	0.32	0.52
Haemoglobin	g/L	Female	10.0	17
Lymphocytes	x10  /L		0.8	
Neutrophil Count	x10  /L		1.5	
Platelet Count	x10  /L		100	550
White Blood Cell Count (WBC)	x10  /L		3	15

Clinical Chemistry				
Laboratory Parameter	Units	Category	Potential Clinical Concern Range	
			Low Flag (< x)	High Flag (>x)
Albumin	mmol/L		30	
Calcium	mmol/L		2	2.75
Creatinine	μmol/L			120
Glucose	mmol/L		3	9
Potassium	mmol/L		3	5.5
Sodium	mmol/L		130	150

Liver Function			
Test Analyte	Units	Category	Potential Clinical Concern Range
ALT/SGPT	U/L	High	$\geq 2x$ ULN
AST/SGOT	U/L	High	$\geq 2x$ ULN
AlkPhos	U/L	High	$\geq 2x$ ULN
T Bilirubin	$\mu\text{mol/L}$	High	$\geq 1.5x$ ULN
T. Bilirubin + ALT	$\mu\text{mol/L}$ IU/L	High	Bilirubin $\geq 1.5x$ ULN AND ALT $\geq 2x$ ULN

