### **COMMENTS REGARDING THE USE OF THESE TABLES**

- Standardized and commonly used toxicity tables (Division of AIDS, National Cancer Institute's Common Toxicity Criteria, and World Health Organization) have been adapted for use by the Division of Microbiology and Infectious Diseases (DAIDS) and modified to better meet the needs of participants in Division of Microbiology and Infectious Diseases (DMID) trials.
- For parameters not included in the following Toxicity Tables, study sites should refer to the "Guide for Estimating Severity Grade" located above.
- Criteria are generally grouped by body system.

Some protocols may have additional protocol-specific grading criteria, which will supersede the use of these tables for specified criteria.

**Note:** Adult DMID toxicity criteria will be applied for all laboratory parameters, with the exception of serum creatinine adolescent laboratory data, which will be assessed using pediatric DMID toxicity criteria. The DMID pediatric toxicity table may be accessed at <https://www.niaid.nih.gov/sites/default/files/dmidpedtox.pdf>.

HEMATOLOGY				
	Grade 1	Grade 2	Grade 3	Grade 4
Hemoglobin	9.5 to 10.5 gm/dL	8.0 to 9.4 gm/dL	6.5 to 7.9 gm/dL	<6.5 gm/dL
Absolute Neutrophil Count	1000 to 1500 /mm 	750 to 999 /mm 	500 to 749 /mm 	<500 /mm 
Platelets	75,000 to 99,999 /mm 	50,000 to 74,999 /mm 	20,000 to 49,999 /mm 	<20,000 /mm 
White Blood Cells	11,000 to 13,000 /mm 	13,000 to 15,000 /mm 	15,000 to 30,000 /mm 	>30,000 or <1000 /mm 
% Polymorphonuclear Leukocytes + Band Cells	>80%	90 to 95%	>95%	N/A
Abnormal Fibrinogen	Low: 100 to 200 mg/dL High: 400 to 600 mg/dL	Low: <100 mg/dL High: >600 mg/dL	Low: <50 mg/dL High: N/A	Fibrinogen associated with gross bleeding or with disseminated coagulation
Fibrin Split Product	20 to 40 mcg/mL	41 to 50 mcg/mL	51 to 60 mcg/dL	>60 mcg/dL
Prothrombin Time (PT)	1.01 to 1.25 × ULN	1.26 to 1.5 × ULN	1.51 to 3.0 × ULN	>3 × ULN
Activated Partial Thromboplastin (APTT)	1.01 to 1.66 × ULN	1.67 to 2.33 × ULN	2.34 to 3 × ULN	>3 × ULN
Methemoglobin	5.0 to 9.9%	10.0 to 14.9%	15.0 to 19.9%	>20%

N/A=not applicable; ULN=upper limit of normal.

CHEMISTRIES				
	Grade 1	Grade 2	Grade 3	Grade 4
Hyponatremia	130 to 135 mEq/L	123 to 129 mEq/L	116 to 122 mEq/L	<116 mEq/L or abnormal sodium with mental status changes or seizures

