### **4.5.3. Additional Safety Assessments**

#### **4.5.3.1. Laboratory Data**

Summary tables for laboratory data (haematology, clinical chemistry) will be produced:

- Change from baseline over time
- Frequency and percentage of laboratory results (relative to Normal Range) post-baseline relative to baseline
- Note: values of PCI will be flagged in listings only.

Separate summary tables for haematology and clinical chemistry laboratory tests will be produced. The following will be presented, at a minimum:

- Haematology parameters (including Platelet count, RBC count, Hemoglobin, Hematocrit, RBC Indices (Mean corpuscular volume (MCV), Mean corpuscular Hemoglobin (MCH), %Reticulocytes), WBC count (Lymphocytes, Neutrophils, Monocytes, Eosinophils, Basophils))
- Clinical chemistry parameters (including Blood urea nitrogen (BUN), Potassium, Sodium, Creatinine, Glucose(non-fasting), AST, SGOT, ALT, SGPT, Alkaline phosphatase, Total and direct bilirubin, calcium & Total Protein)

Additionally, summary tables for urinalysis data will be produced:

- Change from baseline in urine concentrations over time
- Frequency and percentage of urinalysis results post-baseline relative to baseline
- Note: values of PCI will be flagged in listings only.

The following will be presented, at a minimum:

- Urinalysis parameters (Specific gravity, pH, glucose, protein, blood, ketones, bilirubin, urobilinogen, nitrite, leukocyte esterase by dipstick. Microscopic examination (if blood or protein is abnormal), Protein/creatinine ratio)

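### The SAP labels its haemoglobin limits of potential clinical importance g/L, but the numbers fit only g/dL; applied literally to g/L data, the listing flag would be uninformative

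*SAP*

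**What the plan says.** SAP 6.3.1 first classifies laboratory values as high or low against the laboratory's own reference ranges. It then adds a second layer: "the following criteria will be used to flag potential clinical importance". The haematology table in 6.3.1.1 sets the direction of the flags in its header, "Low Flag (< x) High Flag (>x", and gives the haemoglobin row as "Haemoglobin g/L Female 10.0 17". The row above it reads "Haematocrit Ratio of 1 Female 0.32 0.52". No footnote or other unit statement in the SAP alters the haemoglobin row.

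SAP 4.5.3.1 says where the flags appear: "values of PCI will be flagged in listings only".

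The protocol puts haemoglobin on a different scale. Its DMID toxicity table (Appendix 7) reads "Hemoglobin 9.5 to 10.5 gm/dL 8.0 to 9.4 gm/dL 6.5 to 7.9 gm/dL <6.5 gm/dL", running from Grade 1 to Grade 4.

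The clinical chemistry table in SAP 6.3.1.1 also lists albumin, with a low limit of 30 and the unit mmol/L.

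**The concern.** Limits of 10.0 and 17 are on the scale the protocol uses for haemoglobin in g/dL, yet the row says g/L. The unit and both limits sit together in one intact row, so a table broken in extraction is an unlikely explanation.

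The chemistry rows in the same section use SI units (mmol/L for calcium and glucose, μmol/L for creatinine), so a dataset holding haemoglobin in g/L is plausible. A programmer who took the row literally would then produce a flag that is always high and never low.

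Clinically significant change in laboratory values is a secondary safety endpoint, and haemoglobin is a required test (protocol Table 5). The protocol's risk table (2.3.1) also names haemolytic anaemia among the nitrofurantoin risks, so a low-haemoglobin flag that cannot fire would be a relevant loss.

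**Working it through.** **Inputs.** PCI limits: low < 10.0, high > 17, unit g/L (SAP 6.3.1.1). Haemoglobin grade boundaries: 10.5, 9.5, 8.0 and 6.5 g/dL (protocol Appendix 7). Haematocrit limits: 0.32 and 0.52 (SAP 6.3.1.1). Conversion: 1 g/dL = 10 g/L.

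**Step 1: the limits as labelled.** 10.0 g/L ÷ 10 = 1.0 g/dL, and 17 g/L ÷ 10 = 1.7 g/dL. The protocol's Grade 4 cut-off is 6.5 g/dL = 65 g/L. That is 65/10.0 = 6.5 times the SAP's low limit and 65/17 = 3.8 times its high limit. In the stated unit, the SAP's high limit therefore lies far inside the protocol's most severe grade of low haemoglobin.

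**Step 2: apply the flags to g/L data.** The first four rows are the DMID boundaries and the fifth is a Grade 4 value. The remaining rows are illustrative.

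| Hb, g/dL | Hb, g/L | As labelled: low (<10.0) | As labelled: high (>17) | Reconciled: low (<100) | Reconciled: high (>170) |
|---|---|---|---|---|---|
| 10.5 | 105 | no | yes | no | no |
| 9.5 | 95 | no | yes | yes | no |
| 8.0 | 80 | no | yes | yes | no |
| 6.5 | 65 | no | yes | yes | no |
| 6.4 | 64 | no | yes | yes | no |
| 12 | 120 | no | yes | no | no |
| 14 | 140 | no | yes | no | no |
| 16 | 160 | no | yes | no | no |
| 17.5 | 175 | no | yes | no | yes |

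As labelled, every row is flagged high and none low. A low flag would need a result below 1.0 g/dL.

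**Step 3: read the same numbers as g/dL.** The low limit of 10.0 falls inside the protocol's Grade 1 band, and the flags separate low, unremarkable and high values, as the last two columns show.

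**Step 4: a second scale check.** Dividing the haemoglobin limits by the haematocrit limits in the adjacent row gives 10.0/0.32 = 31.3 and 17/0.52 = 32.7. Assuming a usual red-cell haemoglobin concentration of about 32 to 36 g/dL (a figure the documents do not give), these ratios are close to that range in g/dL and tenfold too small in g/L. The conclusion does not depend on this check.

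**Albumin.** A low limit of 30 reads as a g/L value, not a mmol/L value. The documents contain no second albumin figure to test it against, so this rests on the general scale of the analyte. Albumin is not in the routine panel (protocol Table 5), but serum albumin is a required follow-up assessment after a liver stopping event (protocol 10.6).

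**The case against.** The mismatch itself is hard to dispute. The case on the other side is about how much follows from it, and most of that case stands.

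- A reader might infer that every participant will be flagged high. The documents do not support that as a prediction. They do not state the unit in which haemoglobin results are held, and the data-handling conventions sit in the OPS, which is not among the documents. With g/dL data the flags work and only the label is wrong. A high flag on every haemoglobin result would also be conspicuous in a listing.
- A reader might infer that a true fall in haemoglobin would be hidden, or that these flags are how the SAP identifies clinically significant change. Neither follows. SAP 4.5.3.1 includes haemoglobin in the change-from-baseline summaries and in the summaries relative to normal range, and neither uses the 10.0 and 17 limits. Under protocol 8.2.4 the investigator reviews each laboratory report and records clinically significant changes as adverse events. SAP 4.5.2 has those graded by the DMID tables, where haemoglobin is in g/dL.
- The haemolytic anaemia argument is partly mitigated. The protocol links that risk to G6PD deficiency, and exclusion criterion 39 covers known deficiency. Unrecognised deficiency remains possible.
- A reader might conclude that the albumin row should be deleted because albumin is not collected. The liver-event follow-up in protocol 10.6 contradicts that.

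What remains is a row that is wrong as written and a flag that may not work. The listing-only restriction limits the harm, but it also means no summary table of PCI values would expose the error.

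**Conclusion.** The haemoglobin row is wrong by a factor of ten between its unit and its limits. This is certain from the SAP and protocol alone. The consequence is conditional: if results are held in g/L and the limits are applied literally, every realistic value is flagged high and none low in both arms, and the haemoglobin PCI flag carries no information. If results are held in g/dL, the error is one of labelling only.

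The effect is confined to listings. The primary endpoint and the safety summaries and assessments that do not use these limits are unaffected. The row should be corrected because it defines a safety flag and is wrong on its face, not because the safety evaluation as a whole depends on it. The apparent albumin unit error is a reason to check the rest of the table.

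**What to change.** In SAP 6.3.1.1, make the haemoglobin unit and limits agree: either g/dL with 10.0 and 17, or g/L with 100 and 170, whichever matches the unit in the analysis dataset. This reconciles the unit and introduces no new threshold. Correct the albumin unit from mmol/L to g/L and keep the row. Then check the OPS and the programmed limits against the corrected table, and confirm the unit of the haemoglobin variable to which they are applied.

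The cost is two small edits to one SAP section and a short programming check, with no effect on data collection or on any other analysis.

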### 6.3.1.2. ECG

ECG Parameter	Units	Potential Clinically Important Range	
		Lower	Upper
Absolute			
Absolute QTc Interval	msec		>450
Absolute PR Interval	msec	< 110	> 220
Absolute QRS Interval	msec	< 75	> 110
Change from Baseline			
Increase from Baseline QTc	msec		≥ 60

### 6.3.1.3. Vital Signs

Vital Sign Parameter (Absolute)	Units	Potentially Clinically Important Range	
		Lower	Upper
Systolic Blood Pressure	mmHg	< 85	> 160
Diastolic Blood Pressure	mmHg	< 45	> 100
Heart Rate	bpm	< 40	> 110

### 6.3.2. Study Period

Assessments and events will be classified according to the time of occurrence relative to the study intervention period.

**Pre-Intervention** is defined as time prior to the first dose of study intervention.

**On-Intervention** is defined as time from first dose to End of Study (end of all follow up visits). If time of assessment or study intervention is not collected, the following assessment on the first dose date will be assumed to be taken prior to the first dose and therefore considered pre-intervention: ECG, Lab, and vital signs, and first dose date and time is considered the start of on-intervention for AE and concomitant medication.

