Urine pregnancy test (for women of child bearing potential)	X^			X*						X	X@		^ Can be completed as a prescreen if Prescreen ICF signed.  * One on-therapy test should be conducted on D2  @ = If E.D is post Day 6 onward.
Follicle-stimulating hormone and estradiol (as needed in women of non-childbearing potential only)	X												
HIV, Hepatitis B and C monitoring sample collection and assessment of history at screening	X												If test otherwise performed within 3 months prior to first dose of study intervention, monitoring sample at screening is not required.

Cohort 2: Reduced PK  Procedure	Screening # (Day -1 or can be on Day 1)	Cohort 2: Reduced PK Sampling & Clinic Visits and Telephone calls [Days]							ToC (D10 to D13) 5 to 8 days post treatment	E.D.^	Follow-Up (28 ±3 days following first dose)	Notes:
		Outpatient Clinic intervention Period [Days] *= Telephone call day						6				# E-consent may be used
		1 (Pre-Dose)	1 (Post-Dose)	2	3*	4*	5*					^E.D = early discontinuation/withdrawal; see early discontinuation section
Laboratory assessments (haematology, chemistry include liver chemistries and urinalysis)	X*	X		X				X	X	X	*Sample at screening processed by local labs: urine dipsticks (nitrite and leukocyte esterase) can be completed as a prescreen  On therapy samples will be obtained pre-dose. See footnote	
12-lead ECG	X		X					X	X	X	Triplicate ECG at screening and single ECG at all subsequent visits.	
Vital signs	X	X	X	X				X	X	X	Triplicate measurements of blood pressure and pulse rate will be obtained at screening and baseline and averaged. Single measurements will be obtained pre-dose at all other timepoints.	
Randomization		X										

Cohort 2: Reduced PK  Procedure	Screening # (Day -1 or can be on Day 1)	Cohort 2: Reduced PK Sampling & Clinic Visits and Telephone calls [Days]										Notes:	
		Outpatient Clinic intervention Period [Days] *= Telephone call day						6		ToC (D10 to D13) 5 to 8 days post treatment	E.D.^	Follow- Up (28 ±3 days following first dose)	# E-consent may be used  ^E.D = early discontinuation/withdrawal; see early discontinuation section
		1 (Pre- Dose)	1 (Post- Dose)	2	3*	4*	5*						
Genetic sample (optional)		X											Pre-dose (baseline), Germline genetic research may be described in a separate ICF or as part of a combined ICF. A separate signature is required where participant participation is optional.  This sample differs from urine bacterial samples that will be collected for potential genetic analysis.

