- # A site may use an electronic method to obtain participant signature as long as it conforms to 21CFR part 11 and is approved by IRB: Baseline data will be collected at pre dose on Day 1 (except for triplicate ECG which uses Day -1 screening)
- All screening activities to occur with 24 hrs of dosing. Lab results may be extended 24 +6 hrs as long as report assessed prior to dosing.
- The 24 hour screening period starts from the signing of the main ICF.
- Point of Care tests may be utilized when appropriate and describe in Section 10.2 for day -1 screening visit and only on prior agreement with GSK

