### **8.2.3. Electrocardiograms**

- The screening assessment is also considered the baseline assessment.
- Triplicate (screening) and Single (all other study visits unless QTc flag detected) 12-lead ECG will be obtained as outlined in the SoA (see Section 1.3) using an ECG machine that automatically calculates the heart rate and measures PR, QRS, QT, and QTc intervals. Refer to Section 7.1.2 for QTc withdrawal criteria and additional QTc readings that may be necessary.
- At each timepoint at which triplicate ECGs are required, 3 individual ECG tracings should be obtained as closely as possible in succession, but no more than 2 minutes apart.

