#### 4.1.2. Baseline Definition

For all endpoints the baseline value will be the latest pre-dose assessment with a non-missing value, including those from unscheduled visits. If time is not collected, Day 1 assessments are assumed to be taken prior to first dose and used as baseline.

The mean will be considered for triplicate measurements taken at the latest pre-dose assessment. If the latest pre-dose assessment is missing, then the previous assessment time point would be considered as baseline where possible (i.e. if Day 1 (Pre-dose) is missing the Day -1 will be used) unless specified otherwise.

Parameter	Study Assessments Considered as Baseline		Baseline Used in Data Display
	Screening/ Day -1	Day 1 (pre- dose)	
Efficacy			
Microbiological response		x	Day 1(pre-dose)
UTI Clinical Symptom Score Assessment	x	x	Day 1(pre-dose)
CCI			
Quantitative Bacteriology Culture		x	Day 1(pre-dose)
CCI			
Safety			
12-lead ECG	x		Day -1
Vital sign	x	x	Day 1(pre-dose)
Haematology*	x	x	Day 1(pre-dose)
Clinical chemistry*	x	x	Day 1(pre-dose)
Urinalysis*	x	x	Day 1(pre-dose)
PK			
PK urine sample (Cohort 1)		x	Day 1(pre-dose)

Parameter	Study Assessments Considered as Baseline		Baseline Used in Data Display
	Screening/ Day -1	Day 1 (pre-dose)	
PK plasma sample (Cohort 1)		x	Day 1(pre-dose)

\* If baseline data is missing, then change from baseline calculations will not be performed and will be set to missing.

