### 6.3.3. Study Day and Reference Dates

The safety and efficacy reference date is the study intervention start date and will be used to calculate study day for safety and efficacy measures and baseline characteristics, as well as efficacy durations.

The study day is calculated as below:

- Assessment Date = Missing → Study Day = Missing
- Assessment Date < Reference Date → Study Day = Assessment Date – Ref Date
- Assessment Date ≥ Reference Date → Study Day = Assessment Date – Ref Date + 1

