### 6.3.4. Assessment Window

- Actual times will be used in the derivation of PK parameters and in the individual concentration-time plots.
- Planned times will be used in the descriptive summaries and in mean and median plots
- Planned time will be used for all other analysis

For data summaries by visit, scheduled visits with nominal visit description as well as the worst-case post baseline will be displayed. Unscheduled visits will not be displayed or slotted into a visit window but will be included in the derivation of worst-case post baseline assessment. All un-scheduled visits will be displayed in the listing.

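### The missing-time rule in SAP 6.3.2 and 4.1.2 labels the scheduled Day 1 post-dose ECG and post-dose vital signs as pre-dose

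*SAP*

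**What the plan says.** Two SAP sentences deal with missing times. SAP 6.3.2 sorts data into pre-intervention and on-intervention. If either the assessment time or the dose time is missing, an ECG, laboratory result or vital sign on the first-dose date "will be assumed to be taken prior to the first dose and therefore considered pre-intervention: ECG, Lab, and vital signs". SAP 4.1.2, on baseline, says: "If time is not collected, Day 1 assessments are assumed to be taken prior to first dose and used as baseline". Neither sentence excepts an assessment that is scheduled after dosing.

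Other text points elsewhere. For everything outside PK parameters and concentration displays, SAP 6.3.4 says: "Planned time will be used for all other analysis". The table in SAP 4.1.2 gives screening (Day -1) as the only ECG baseline and shows Day 1 pre-dose as the baseline for vital signs. The protocol agrees on ECG. Section 8.2.3 states "The screening assessment is also considered the baseline assessment", and the Cohort 2 schedule footnote reads "Baseline data will be collected at pre dose on Day 1 (except for triplicate ECG which uses Day -1 screening)". The Cohort 1 footnote has the same effect.

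In the Schedule of Activities for both cohorts, Day 1 laboratory samples are marked before dosing only. The ECG has no Day 1 pre-dose mark, and its Day 1 mark is in the post-dose column. Vital signs are marked in both columns.

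**The concern.** A missing-time default should be right in the cases where it is used. For a scheduled Day 1 ECG that is not the screening ECG, this default is wrong every time. For vital signs it is wrong for one of the two Day 1 sets. The trigger is also broad: one missing dose time relabels both the ECG and the post-dose vital signs of that participant, even if those readings were themselves timed.

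No SAP text says whether 6.3.2 or 6.3.4 prevails, or whether the table or the general sentence governs within 4.1.2. Two programmers could each follow the SAP and produce different safety tables. Changes from baseline in vital signs and ECG are named secondary endpoints, so the handling should be settled before treatment codes are known.

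**Working it through.** The plan gives no figure to reproduce, so the check sets the schedule against the rules. The schedule entries are the same in both cohorts.

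| Day 1 assessment | Scheduled | 6.3.2 if a time is missing | 6.3.4 planned time | Baseline in 4.1.2 table |
|---|---|---|---|---|
| Laboratory | pre-dose only | pre-intervention | pre-dose | Day 1 pre-dose |
| ECG (not screening) | post-dose only | pre-intervention | post-dose | screening / Day -1 |
| Vital signs, pre-dose set | pre-dose | pre-intervention | pre-dose | Day 1 pre-dose |
| Vital signs, post-dose set | post-dose | pre-intervention | post-dose | not a baseline |

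The rules agree for rows one and three and disagree for rows two and four. The schedule's note on vital signs says single readings are otherwise taken before dosing, which does not fit the post-dose mark. I take the mark as the schedule.

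**ECG.** Baseline stays at the screening triplicate, so the error is confined to the study-period label. SAP 4.5.3.3 defines the maximum QTc and maximum QTc increase tables as post-baseline. The Day 1 value is lost only if they are programmed on on-intervention records. Scheduled ECGs after the first dose, early discontinuation aside, are:

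- Cohort 1: Day 1 post-dose, Day 4, ToC, Follow-up = 4.
- Cohort 2: Day 1 post-dose, Day 6, ToC, Follow-up = 4 (Day 6 as described in the Amendment 5 summary).

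So 1 of 4 scheduled values is exposed in each cohort. Counting only ECGs between first and last dose, it is 1 of 2 in Cohort 1 (Day 4 remains) and 1 of 1 in Cohort 2.

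Illustration with assumed values: screening mean 420 msec, untimed Day 1 post-dose 485, Day 6 425, later readings no higher.

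- Day 1 kept: max(485, 425) - 420 = 65 msec.
- Day 1 excluded: 425 - 420 = 5 msec.
- Listing criteria in SAP 6.3.1.2: 485 > 450, and 65 ≥ 60. Both are met.

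**Vital signs.** The general rule in 4.1.2 takes the latest pre-dose value. If the post-dose set is deemed pre-dose, it can be that latest value and displace the pre-dose triplicate mean, although 4.1.2 also says "The mean will be considered for triplicate measurements taken at the latest pre-dose assessment". SAP 6.3.5 covers repeated ECGs and laboratory tests but gives no rule for choosing between two vital-signs sets.

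Illustration with assumed systolic values: pre-dose triplicate mean 118 mmHg, untimed post-dose 130, Day 2 120.

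- Correct baseline: 120 - 118 = +2 mmHg.
- Post-dose reading as baseline: 120 - 130 = -10 mmHg.
- Every later change for this participant moves by 118 - 130 = -12 mmHg.

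**Screening on Day 1.** The schedule allows this. Under SAP 6.3.3, "The safety and efficacy reference date is the study intervention start date", so the screening triplicate and the post-dose ECG both have study day 0 + 1 = 1. Study day does not separate them, but the visit label does. An untimed screening triplicate on that date really is pre-dose, so a label-based rule handles both readings correctly.

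**The case against.** The best defence is that the specific text already gives the right answer. The 4.1.2 table names Day 1 pre-dose as the vital-signs baseline, and under planned time a set labelled post-dose cannot be that. The QTc tables are post-baseline rather than on-intervention. With baseline at screening, a Day 1 post-dose ECG is post-baseline whatever its study-period label. The ECGs also differ in format: "Triplicate ECG at screening and single ECG at all subsequent visits".

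The trigger may be rare as well. Protocol 6.4 has in-clinic dose times recorded in Cohort 1, and the Cohort 2 diary captures date and time of dosing. Nothing suggests that ECG or vital-sign times go uncollected. Further data-handling conventions sit in the Output and Programming Specification, which is not available here and may settle the matter. The safety analysis is descriptive, and the primary endpoint is untouched.

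Most of this stands as a limit on impact. It does not remove the error: 6.3.2 is an explicit rule with no exception, and the SAP nowhere says that the table or 6.3.4 overrides it.

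A reader might infer three stronger points that the documents do not support:

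- That an untimed Day 1 ECG becomes the QTc baseline. The 4.1.2 table, Protocol 8.2.3 and the schedule footnotes all fix baseline at screening.
- That a QTc rise would go unseen. Loss from the summary tables is possible but not established, and the listings flag both the absolute value and the rise.
- That QTc stopping decisions are affected. Under Protocol 7.1.2 the investigator acts on the ECG when it is taken, independently of SAP labels.

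**Conclusion.** The missing-time rule is wrong for the scheduled Day 1 ECG and for the Day 1 post-dose vital-signs set, and right for laboratory data. For ECG the consequence is a wrong study-period label and, under one programming choice, a value missing from the maximum QTc tables. For vital signs the consequence can be a wrong baseline for that participant, although the 4.1.2 table and 6.3.4 point the other way.

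This is a minor correction. The documents give no rate of missing times, so the number affected is unknown. It is probably small, out of at most 122 (possibly 141) randomized across both cohorts and arms. The conclusion rests on the schedule marks as read above. The msec and mmHg examples use assumed values and show direction only.

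**What to change.** Amend SAP 6.3.2 and 4.1.2 before unblinding to state that:

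- when an assessment or dose time is missing, ECGs and vital signs are classified by scheduled timepoint label, so that Day 1 post-dose is on-intervention and post-baseline;
- the pre-dose default applies only to assessments scheduled before dosing;
- the 4.1.2 table overrides the general sentence: ECG baseline is the screening triplicate, including when screening is on Day 1, and vital-signs baseline is Day 1 pre-dose.

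An unscheduled Day 1 reading with no time has no label. Query the site and, if the time stays unknown, do not use the reading as baseline.

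The cost is a sentence or two in each section and a matching check of the programming specification. It needs no new data, visit or ECG.
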